RBC turnover and provide viable alternatives to HbA1c as a marker of glycemia. In particular, these biomarkers are not based on hemoglobin and hence, do not depend on RBC turnover (26). Since fructosamine reflects the average levels of blood glucose during the former 1 to 3 weeks, fructosamine also mirrors a poorly controlled glucose metabolism better than HbA1c (27). However, some physiological and pathological conditions can significantly influence the metabolism of fructosamine. In brief, all those clinical conditions that affect protein metabolism potentially influence the concentrations of glycosylated proteins (28). Thus, physiologic or pathologic conditions linked to hypo-proteinemia (i.e., pregnancy or malnutrition) are more likely to affect the concentration of fructosamine. Another disadvantage of fructosamine is that its concentration is considerably influenced by the levels of immunoglobulins, especially IgA, which are present in abnormal concentration in a broad range of clinical conditions.(29).

Among women who experience glucose abnormalities during pregnancy, screening during the postpartum period offers a window of opportunity for early identification of diabetes and prediabetes. The rates of postpartum T2D screening with an OGTT for women with GDM are not optimal given the majority of women with GDM fail to return for postpartum glucose testing. A new device called a continuous glucose monitor or “CGM” is a small disc that is placed on the arm and can be easily placed and removed by the person wearing it. It is worn for 10 days and can stay in place for activities such as sleeping and showering. Over 10 days, over 1000 sugar measurements are taken without the person wearing the device having to do any testing (30). Continuous glucose monitoring (CGM) systems have been recognized as an ideal method of monitoring glycemic control in diabetic patients (30,31). The data of rigorous 24 h glucose profiles from CGM allow the calculation of glycemic variations, detection of asymptomatic hypoglycaemia and accurately depict the characteristics of blood glucose fluctuations (30,31). In the past decade, CGM has been proven to have similar accuracy to self-monitoring of blood glucose (SMBG) and yet provides better therapy optimization and detects trends in glucose values due to higher frequency of testing. Although CGM has been used successfully in T1D and T2D patients (31), the effectiveness of CGM in improving pregnancy outcomes

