#### STUDY OBJECTIVE

Given the damaging effect of prolonged undetected hyperglycemia, prevention and early diagnosis of T2D is cost-saving and of public health importance. This research study is being done to assess if using a glucose sensor (also known as a continuous glucose monitor or CGM) after childbirth can help identify women who are at risk of developing diabetes after having diabetes during pregnancy or gestational diabetes. Currently, screening for diabetes after childbirth is performed with an oral glucose tolerance test 4-16 weeks after delivery, but this is burdensome and most patients are non-compliant. This study will use a CGM worn on the skin for 10 days. The data from the sensor will be compared to the standard oral glucose tolerance test as well as a HbA1c and fructosamine test. This is a single site study from patients with recent GDM that attended the diabetes clinic at Woman's Hospital. The research team plans to enroll 50 participants aged 18 years or older into the study. Participation in the study is expected to last up to 10 days during the postpartum interval. Study procedures include; 1) consent and screening; and 2) sensor placement and download after 10 days of wear postpartum during which an OGTT, fructosamine and HbA1c test will be administered.

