#### HbA1c, Fructosamine and OGTT data

We will use the glucose levels and HbA1c values as defined by the American Diabetes Association (ADA) guidelines(8) for the diagnosis of normal, prediabetes, and type 2 diabetes. Following the guidelines of ADA, a fasting blood glucose (FBG) below 126 or 2-h blood glucose (2hBG) < 140 mg/dl is considered normal glucose tolerance; FBG of 100-125 mg/dl or 2-h blood glucose (2hBG)  $\geq$  140- 199 mg/dl is classified as prediabetes, and FBG above or equal to 126 mg/dL or 2-h blood glucose (2hBG)  $\geq$  200 mg/dl in a standard oral glucose tolerance test (OGTT) as diabetic. The reference ranges for HbA1c results are:

- No diabetes: below 5.7%
- Borderline/prediabetes: 5.7% to 6.4%
- Diabetes: 6.5% or higher (8)

Fructosamine results may be considered alongside the HbA1c and other tests.

- In non-diabetics with normal albumin, fructosamine levels normally range between 175-265umol/L (micromoles per liter). For people with uncontrolled diabetes, the fructosamine range is 268-870 millimoles per liter (mmol/L). The concentrations of fructosamine corresponding prediabetes and diabetes clinical cut-points of 5.7% and 6.5% for HbA1c, based on percentiles, were 241.4 umol/L (the 77.1 percentile) and 270.2 umol/L (the 96.5 percentile), respectively (36).

Collection of glucose data The blinded glucose monitoring data on glycemia will be retrospectively assessed. The participant data collected from the CGM (Dexcom G7) will be downloaded with the Dexcom G7 reader and uploaded to Dexcom CLARITY

The percentage of time-in-target range, time hypoglycemia, and time hyperglycemia will be reported as either means with standard deviations (SD) or medians with interquartile ranges (IQR), depending on variable distribution. For analyses assessing overnight glycemia, daytime is defined as 5:00 AM to 11:59 PM and nighttime as 12:00 midnight to 4:59 AM

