#### Statistical analysis

Statistical analyses will be performed using SPSS version 15.1 for Windows (SPSS, Inc.; Chicago, IL). Continuous variables will be tested for normality of distribution using the Kolmogorov-Smirnov test. When necessary, non-normally distributed data will be subjected to logarithmic or square-root transformation to obtain a normal distribution where necessary for subsequent analyses. Continuous parameters will be given as means  $\pm$  standard deviations or medians with interquartile ranges (IQR). Results will be presented as mean  $\pm$  standard deviation for normally distributed continuous variables and as medians, with the 25th and 75th IQR for non-normally distributed variables. Categorical data will be presented as percentage. Pearson correlation coefficient ( $r$ ) and the significance for it ( $p$ ) will be calculated between the variables. The chi square test will be used to compare categorical variables. Chi-square test will be used to test differences in percentage proportionality Student t tests will be used to compare normally distributed groups; otherwise, Mann-Whitney rank sum tests will be used. Multiple groups will be compared using Kruskal-Wallis one-way ANOVA with a Dunn's test for pairwise comparisons when appropriate. A two-sided P-value  $< 0.05$  is considered statistically significant.

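### Does a fructosamine range printed in mmol/L, beside two sets of values with no rule for choosing between them, put any planned analysis at risk?

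*Combined protocol and SAP*

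**What the plan says.** All the interpretive values for fructosamine stand in one bullet of the section on HbA1c, fructosamine and OGTT data. It opens with a reference range: "In non-diabetics with normal albumin, fructosamine levels normally range between 175-265umol/L (micromoles per liter". The next sentence gives the range at issue: "For people with uncontrolled diabetes, the fructosamine range is 268-870 millimoles per liter (mmol/L". Last come the fructosamine equivalents of HbA1c 5.7% and 6.5%, which "were 241.4 umol/L (the 77.1 percentile) and 270.2 umol/L (the 96.5 percentile), respectively", cited to reference 36.

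The same section adopts ADA definitions of normal, prediabetes and diabetes for glucose and HbA1c. For fructosamine it says only: "Fructosamine results may be considered alongside the HbA1c and other tests".

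Two other places bear on the point. The Study Objective makes fructosamine a comparator: "The data from the sensor will be compared to the standard oral glucose tolerance test as well as a HbA1c and fructosamine test". The Statistical analysis section lists methods without naming variables: Pearson correlation, t or Mann-Whitney tests, Kruskal-Wallis tests, and for categories, "The chi square test will be used to compare categorical variables".

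**The concern.** The unit is wrong on its face. It is written in words and as a symbol, so a misread character in the PDF does not explain it. The sentence also has no citation of its own against which a reader could check it.

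The second worry is that the bullet offers two sets of values and does not choose. A woman at 250 umol/L lies inside the non-diabetic range and above the prediabetes equivalent. Fructosamine is a named comparator, and chi-square tests are planned for categorical variables that are not listed, so a categorised fructosamine is neither promised nor excluded. If categories were formed, the cut-point could be picked once the data were in hand, and the share of women labelled abnormal would depend heavily on that pick.

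**Working it through.** **Inputs.** From the section on HbA1c, fructosamine and OGTT data: 175-265 umol/L (non-diabetic); 268-870 mmol/L as printed (uncontrolled diabetes); 241.4 umol/L at the 77.1 percentile and 270.2 umol/L at the 96.5 percentile. From the Study Objective: 50 women.

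**Step 1, the unit.** 1 mmol/L = 1,000 umol/L, so 268-870 mmol/L = 268,000-870,000 umol/L. Then 268,000 / 265 = 1,011 and 268,000 / 270.2 = 992. Taken as umol/L, the lower end (268) falls between 265 and 270.2. The digits fit and only the unit does not.

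**Step 2, does any analysis use the range?** The Statistical analysis section refers to no fructosamine range or cut-point. If fructosamine enters the Pearson correlation, its measured values are used, and the printed range plays no part. The same holds for a t test or a rank test on the measured values.

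**Step 3, the two sets compared, with the unit read as umol/L.**

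| Interval (umol/L) | Width | Descriptive ranges | HbA1c-matched values |
|---|---|---|---|
| 241.4-265 | 23.6 | non-diabetic | prediabetes band |
| 265-268 | 3.0 | in neither | prediabetes band |
| 268-270.2 | 2.2 | uncontrolled diabetes | prediabetes band |

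The first row is not a contradiction: a woman with prediabetes is not diabetic, so both descriptions can be true of her. Only the last row gives conflicting diabetes labels.

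**Step 4, size if both sets were used as cut-points.** This describes the cited reference population only.

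- Upper bound: 96.5% - 77.1% = 19.4% lie in 241.4-270.2.
- Linear interpolation: 23.6 / 28.8 = 0.819, and 0.819 x 19.4% = 15.9% lie in 241.4-265.
- Normal curve through both percentiles: z(0.771) = 0.742 and z(0.965) = 1.812. SD = 28.8 / (1.812 - 0.742) = 26.9; mean = 241.4 - 0.742 x 26.9 = 221.4. This puts 17.6% in 241.4-265, 1.1% in 265-268 and 0.7% in 268-270.2.
- Lognormal curve: 17.7%, 1.0% and 0.6%.

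If that distribution held here, 0.176 x 50 = 8.8, or about 9 women, would lie in the overlap. The documents give no fructosamine distribution for women 4-16 weeks after delivery, so this count is an illustration only.

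**The case for a change.** The strongest case for a change is that this bullet is the only place where the plan interprets a named comparator, that it contains a certain error, and that one sentence could close the gap. The wording is also loose: the HbA1c list in the same section labels values below 5.7% as no diabetes, which suggests that the authors may sometimes mean non-diabetic to exclude prediabetes. If categories were formed, 22.9% of the reference population would lie above 241.4 but only about 5% to 7% above 265, so the choice would matter.

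The error and the looseness stand. The harm does not follow from them. It needs two steps that the plan does not take: forming fructosamine categories, and using a descriptive reference range as a cut-point. The section commits to diagnostic classes for glucose and HbA1c and gives fructosamine a supporting role. The Background also warns that protein-related conditions ("i.e., pregnancy or malnutrition) are more likely to affect the concentration of fructosamine") disturb this marker, which is a reason to read both sets as context. An analyst who did want classes would find only one set tied to the 5.7% and 6.5% cut-points already in the section.

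A larger remedy, such as an ROC curve for fructosamine against the OGTT, would correct neither the unit nor the overlap. It would need a choice of where to split a three-level OGTT result. It would also rest on OGTT classes that conflict as printed, since fasting glucose of 100-125 mg/dl meets both the normal and the prediabetes descriptions. That is a separate matter.

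**Conclusion.** The unit is a clerical slip by a factor of 1,000 in a descriptive sentence. It can be put right against its source whenever the document is next edited, and no estimate, test or classification in the plan depends on it. The missing rule for fructosamine categories is a gap that analysts can fill sensibly by keeping the marker continuous or by using the HbA1c-matched pair. It affects only an analysis that is not stated.

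The conditional size is 15.9% to 17.7% of the reference population in the overlap and about 0.7% with conflicting diabetes labels. Both figures rest on assumed shapes between two printed percentiles and do not carry over to this cohort without data. The conclusion also assumes that fructosamine is not categorised, which the text implies but does not say outright. No change to the plan follows.

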#### Statistical analysis

Statistical analyses will be performed using SPSS version 15.1 for Windows (SPSS, Inc.; Chicago, IL). Continuous variables will be tested for normality of distribution using the Kolmogorov-Smirnov test. When necessary, non-normally distributed data will be subjected to logarithmic or square-root transformation to obtain a normal distribution where necessary for subsequent analyses. Continuous parameters will be given as means  $\pm$  standard deviations or medians with interquartile ranges (IQR). Results will be presented as mean  $\pm$  standard deviation for normally distributed continuous variables and as medians, with the 25th and 75th IQR for non-normally distributed variables. Categorical data will be presented as percentage. Pearson correlation coefficient ( $r$ ) and the significance for it ( $p$ ) will be calculated between the variables. The chi square test will be used to compare categorical variables. Chi-square test will be used to test differences in percentage proportionality Student t tests will be used to compare normally distributed groups; otherwise, Mann-Whitney rank sum tests will be used. Multiple groups will be compared using Kruskal-Wallis one-way ANOVA with a Dunn's test for pairwise comparisons when appropriate. A two-sided P-value  $< 0.05$  is considered statistically significant.

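### One Kolmogorov-Smirnov test, variant unstated, decides transformation, summary statistic and test choice; it is weak for moderately skewed CGM percentages at n = 50, and the planned transformations do not suit those percentages

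*Combined protocol and SAP*

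**What the plan says.** The normality check is in the Statistical analysis section: "Continuous variables will be tested for normality of distribution using the Kolmogorov-Smirnov test". No variant, separate significance level or graphical check is given. The only level stated is the general two-sided P < 0.05 that "is considered statistically significant".

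Three decisions follow from the result:

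- Transformation: "non-normally distributed data will be subjected to logarithmic or square-root transformation to obtain a normal distribution where necessary for subsequent analyses".
- Summary: mean ± SD for variables taken as normal, median with quartiles otherwise.
- Two-group test: "Student t tests will be used to compare normally distributed groups; otherwise, Mann-Whitney rank sum tests will be used".

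The only correlation listed is Pearson's. No rank alternative is offered, and nothing is said about what happens if a transformation fails to produce normality.

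The section HbA1c, Fructosamine and OGTT data applies the same kind of rule to the sensor metrics: "The percentage of time-in-target range, time hypoglycemia, and time hyperglycemia will be reported as either means with standard deviations (SD) or medians with interquartile ranges", "depending on variable distribution". Comparisons of several groups are rank-based whatever the normality result: "Multiple groups will be compared using Kruskal-Wallis one-way ANOVA with a Dunn's test for pairwise comparisons when appropriate".

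On sample size, the Study Objective section says: "The research team plans to enroll 50 participants aged 18 years or older into the study".

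**The concern.** The textbook Kolmogorov-Smirnov critical value assumes that the mean and SD of the reference normal are known in advance. Here they would have to be estimated from the same women. The fitted curve then lies closer to the data than the critical value allows for, and the test hardly ever rejects. The Lilliefors version corrects this. The plan does not say which version will be used, so the behaviour of the gatekeeper is unknown.

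Percentages of time in, above or below range are bounded. If most women have little dysglycemia, the values would crowd near 100% or 0% and be skewed. Skew that goes unflagged would be summarised as mean and SD and enter Pearson correlation untransformed. This matters because the study's aim is to compare sensor data with the OGTT, HbA1c and fructosamine, and correlation is one of the main tools listed for that.

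The second problem lies downstream of the test. Log and square root pull in a long right tail. Time in range near a ceiling has a long left tail, and a woman with no time in hypo- or hyperglycemia has a value of 0, for which the log does not exist.

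**Working it through.** **Inputs from the documents.** n = 50; two-sided 0.05 (assumed to apply to the normality test as well); Kolmogorov-Smirnov, variant unstated; log or square root if flagged; Pearson. The documents give no power calculation and no expected distribution for any CGM metric, so there is no stated figure to reproduce.

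**Assumptions.** Beta shapes for the percentages, one zero-heavy shape (40% zeros plus an exponential) and lognormals, chosen to span a range. For correlation, a latent correlation of 0.35.

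**Step 1: the statistic.** With z = (x − mean)/SD from the sample, sorted, D is the largest of i/n − Φ(z_i) and Φ(z_i) − (i − 1)/n over all i. At n = 50 the uncorrected 5% critical value is 0.1884. The Lilliefors value, simulated from normal samples, is 0.1246. The gap between the two is why the uncorrected test rejects about 0% of truly normal samples instead of 5%.

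**Step 2: detection rates at n = 50** (simulation, 20,000 samples per shape for Kolmogorov-Smirnov).

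| Assumed shape | Skew | Uncorrected | Lilliefors | Shapiro-Wilk |
|---|---|---|---|---|
| Normal | 0 | 0.0% | 5.0% | 4.9% |
| Time in range, mean 67%, beta(8,4) | −0.4 | 0.1% | 11% | 15% |
| Time in range, mean 80%, beta(12,3) | −0.7 | 0.6% | 26% | 51% |
| Time in range, mean 90%, beta(18,2) | −1.1 | 3% | 56% | 88% |
| Time in range, mean 95%, beta(30,1.5) | −1.5 | 11% | 79% | 98% |
| Time in range, mean 95%, beta(19,1) | −1.7 | 28% | 94% | 99.9% |
| Time above range, mean 5%, beta(0.5,9.5) | 2.3 | 89% | 100% | 100% |
| 40% zeros plus exponential | 2.4 | 99% | 100% | 100% |
| Time below range, mean 1%, beta(0.5,49.5) | 2.7 | 93% | 100% | 100% |

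Rates fall in smaller samples or subgroups. For time in range with mean 91%, beta(20,2), Lilliefors detects 58% at n = 50, 42% at n = 35, 31% at n = 25 and 22% at n = 17. The last is close to 35% of 50 (0.35 × 50 = 17.5). That 35% is the Background section's general OGTT compliance figure, not the study's own assumption.

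**Step 3: what a missed flag does to the summary.** For beta(19,1), SD = √[19 × 1/(20² × 21)] = 0.0476. Mean + 2 SD = 95 + 2 × 4.76 = 104.5%, which is not a possible value.

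**Step 4: what a correct flag does.** For beta(18,2), skew goes from −1.11 to −1.26 after square root and −1.42 after log. For beta(19,1) it goes from −1.71 to −1.84 and −1.99. Both transformations make matters worse, so a better normality test alone does not help time in range.

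**Step 5: correlation power under the plan's two-step rule** (transform if flagged, then Pearson).

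- Lognormal, log-SD 0.75 to 1.25, uncorrected test: 68–71%, against about 66% for Spearman. No loss.
- Moderate right skew, Shapiro-Wilk in place of the uncorrected test: 68% to 72% in one case and 65% to 69% in another, a gain of about 4 points each.
- Strong left skew: 64% for beta(19,1) and 57% for beta(9.5,0.5), against 66% for Spearman. Losses are 66 − 64 = 2 and 66 − 57 = 9 points.
- Truly normal data: Pearson 72%, Spearman 67%. Fixing Spearman costs 72 − 67 = 5 points.

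**The case against.** A reader might infer that the test has almost no ability to detect skew at n = 50, so that skewed data will generally pass as normal. The documents do not support that. They do not say the test will be uncorrected, and an unnamed variant is an ambiguity, not a demonstrated error. With Lilliefors, the strongly skewed percentage shapes in the table are caught 94–100% of the time, and the most skewed ones 89–99% even uncorrected.

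A reader might also infer a loss of 5–18 points of correlation power, by comparing Pearson on raw lognormal data (62%, 54%, 47% at log-SD 0.75, 1.0, 1.25) with Spearman (67%, 67%, 65%). That is not the plan's loss, because the plan transforms flagged data. The most skewed cases, where raw Pearson does worst, are also those most often flagged: uncorrected, 80% at log-SD 1.0 and 96% at 1.25. For the time-in-range shapes beta(19,1) and beta(18,2), even Pearson that is never transformed has 64% and 68% power, against 66% for Spearman in both.

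Two further points stand. The plan defines three glycemic classes, and comparisons across them would use Kruskal-Wallis whatever the normality test says. Median (IQR) is already permitted for the CGM percentages, and that sentence does not tie the choice to Kolmogorov-Smirnov alone.

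What the objection does not remove is the unnamed variant, the weaker detection of moderate skew, transformations that do not suit bounded percentages, and the lack of a rank fallback for Pearson.

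**Conclusion.** The point holds as a minor one. The plan rests three decisions on a test whose variant it does not name. If uncorrected, that test has a level near 0% and detects the assumed time-in-range shapes with skew of −1.1 to −1.7 about 3–28% of the time. If corrected, it copes with the strongest skew but trails Shapiro-Wilk at moderate skew (56% against 88% at a mean of 90%). The planned transformations cannot repair left-skewed time in range, and log fails at 0%.

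The likely consequences are near-ceiling percentages reported as mean and SD, and a small loss of correlation power: about 0–4 points, up to about 9 for extreme left skew. The multi-group comparisons are not touched. Every size quoted depends on assumed shapes and, for power, on an assumed latent correlation of 0.35. The ranking of the tests for skewed data was the same across all the shapes tried, apart from the most extreme, where they all detect nearly everything.

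**What to change.** In the Statistical analysis section, replace Kolmogorov-Smirnov with Shapiro-Wilk plus a Q-Q plot for the continuous variables that remain subject to a normality check. For time in range, time in hypoglycemia and time in hyperglycemia, drop the pre-test and prespecify median (IQR) and Spearman correlation. Amend the reporting sentence in HbA1c, Fructosamine and OGTT data to match. The second change matters more for time in range, since better detection followed by log or square root does not help there.

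The cost is a sentence or two of text and no new data. The statistical price is about 5 points of power for Spearman if a metric turns out to be truly normal (72% to 67% in the case worked above).

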complicated by GDM is still understudied (32). Current updated evidence suggests that CGM is superior to SMBG among GDM pregnancies in terms of detecting hypoglycemic and hyperglycemic episodes, which might result in an improvement of maternal and fetal outcomes (33). In addition, CGM is effective at capturing gestational glucose profiles and improving treatment effect among pregnant women with GDM (34,35). Further research is needed to explore the clinical utility such screening and predictive values of CGM for glucose impairment after having diabetes during pregnancy. We need to improve diabetes testing after childbirth in women who experienced gestational diabetes. This will allow us to target our efforts to improve the early diagnosis and treatment of diabetes following GDM. No studies conducted to date have not comprehensively examined whether CGM after delivery can be used in women with a recent history to predict their risk of diabetes.

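### The study asks whether CGM can screen for postpartum dysglycemia, but the plan tests only association and group differences, with no accuracy measure, CGM cut-off or confidence interval

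*Combined protocol and SAP*

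**What the plan says.** The Background gives the research need as the "clinical utility such screening and predictive values of CGM for glucose impairment after having diabetes during pregnancy". The Study Objective asks whether CGM "can help identify women who are at risk of developing diabetes after having diabetes during pregnancy or gestational diabetes", and adds: "The data from the sensor will be compared to the standard oral glucose tolerance test as well as a HbA1c and fructosamine test". Fifty women are to be enrolled, and "Participation in the study is expected to last up to 10 days during the postpartum interval".

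The inferential methods in the Statistical analysis section are:

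- correlation: "Pearson correlation coefficient ( $r$ ) and the significance for it ( $p$ ) will be calculated between the variables";
- categorical data: "The chi square test will be used to compare categorical variables";
- two groups: t test or Mann-Whitney;
- more than two groups: Kruskal-Wallis with Dunn's test.

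All are at two-sided 0.05. The variable pairs and the groups are not named. The section on HbA1c, fructosamine and OGTT data gives categories for OGTT and HbA1c and cut-points for fructosamine. For CGM it gives only descriptive time-in-range summaries, with no glucose limits and no rule for a positive result.

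**The concern.** A screening question asks how many affected women the test finds, how many unaffected women it wrongly flags, and how precisely those shares are known. The planned tests ask whether CGM and OGTT results are related, or whether CGM differs on average between groups. Those are valid analyses of a different question, and a clear yes to them can coexist with a test that misses half the cases.

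The protocol applies the stricter standard to HbA1c: the Background faults it for false negatives in 60–70% of the cases that the OGTT detects. No matching figure is planned for CGM. With no metric or cut-off named in advance, any accuracy figure reported later would rest on choices made after the data were seen, and a cut-off tuned to the same 50 women tends to flatter the test.

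**Working it through.** The plan contains no accuracy calculation, and its sample size of 50 comes without power, effect size or precision target. There is therefore no stated figure to reproduce. The check is how poor a screen could still be significant under each planned test.

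**Inputs.** N = 50 (Study Objective). Two-sided alpha 0.05 (Statistical analysis). Dysglycemia 30% (Background), so 0.30 × 50 = 15 cases and 35 non-cases. The 30% is used here as an assumption and is varied below.

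**Pearson correlation.** The smallest significant r is t/√(t² + N − 2). With t = 2.011 on 48 df, this is 2.011/√(4.043 + 48) = 0.279, or r² = 0.078. To turn r into accuracy, assume bivariate normality and call the top 30% of the OGTT variable cases. By simulation, r = 0.28 gives:

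- AUC 0.63;
- specificity 36% at 80% sensitivity;
- PPV = 0.30 × 0.80 / (0.30 × 0.80 + 0.70 × 0.641) = 0.240/0.689 = 35%, against a base rate of 30%.

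At 20% to 40% prevalence the AUC is 0.64 to 0.63 and the specificity 37% to 35%. Even r = 0.5 gives an AUC of only about 0.74 and 53% specificity at 80% sensitivity.

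**Mann-Whitney.** U divided by the number of case/non-case pairs estimates the AUC. For 15 v 35 the exact test is significant when the smaller U is at most 169 of 525, so from AUC = 1 − 169/525 = 0.678. Under an equal-variance binormal model, d = √2 × Φ⁻¹(0.678) = 0.65, and specificity at 80% sensitivity is Φ(0.65 − 0.84) = about 43%. The threshold depends on the case count:

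| Cases v non-cases | Smallest significant AUC | Specificity at 80% sensitivity |
|---|---|---|
| 20 v 30 | 0.67 | 41% |
| 15 v 35 | 0.68 | 43% |
| 10 v 40 | 0.70 | 46% |
| 5 v 45 | 0.77 | 59% |

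**Chi-square of CGM result by OGTT status.** Suppose 7 of 15 cases are CGM-positive and 30 of 35 non-cases CGM-negative. The uncorrected chi-square is 6.04, p = 0.014 (Yates 0.036, Fisher 0.027). Sensitivity is 7/15 = 47% (exact 95% CI 21% to 73%), and 8 of 15 cases are missed.

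**What accuracy reporting would give at N = 50.**

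- Sensitivity 12/15 = 80%, exact 95% CI 52% to 96%.
- Specificity 28/35 = 80%, CI 63% to 92%.
- With 7 false positives and 3 false negatives, PPV 12/19 = 63% (38% to 84%) and NPV 28/31 = 90% (74% to 98%).
- AUC 0.80, with Hanley-McNeil SE 0.075, so 0.80 ± 1.96 × 0.075 = 0.65 to 0.95.
- At 80% sensitivity the interval runs from 28–99% with 5 cases (4/5) to 56–94% with 20 cases (16/20).
- If only 35% completed the OGTT, the Background's figure for routine compliance, about 18 women and 5 cases would remain, again giving 28% to 99%.

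**The case against.** This is a small observational study with no stated hypothesis, success criterion or explicit claim that CGM will replace the OGTT, and the phrase about predictive values sits in a Background sentence on research needs. That softens the reading. But the Study Objective is itself about identifying women at risk, against the OGTT as comparator and with the OGTT's burden as the reason for the study.

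The planned methods also come close. Mann-Whitney U rescales to the empirical AUC, and row percentages of a CGM-by-OGTT table are sensitivity and specificity. This is true, but the plan names no CGM metric, no positive rule, no grouping and no interval, so a reader following it would report p-values.

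The table of contents lists *Outcome Measures*, yet no section with that heading appears in the supplied text, so a metric might be named elsewhere. That limits certainty about the metric. The Statistical analysis section reads as complete and contains no accuracy statistic.

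The worked cases are constructions, since the plan does not say what each test will compare, and Kruskal-Wallis was not worked through. A weaker chi-square example, with 6 of 15 cases detected and 30 of 35 non-cases negative, reaches p = 0.044 uncorrected but 0.065 by Fisher, so it carries no weight here.

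Finally, accuracy estimates from 50 women will not settle whether CGM can screen: an interval of about ±10 points around 80% sensitivity needs 1.96² × 0.8 × 0.2/0.10² = 62 cases, or about 207 women at 30%. That is a reason to show the uncertainty.

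**Conclusion.** The concern holds and should be fixed before the masked CGM data are analysed. Followed exactly, the plan yields p-values that cannot answer its only stated objective. With 15 cases among 50 women, significance is reached at an AUC of about 0.63 (Pearson) or 0.68 (Mann-Whitney), and in a table that misses 8 of 15 cases.

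The absence of accuracy measures is read directly from the text. The sizes rest on the 30% prevalence, on all 50 women having an OGTT result, and on normal models for converting r or AUC into specificity. Changing prevalence from 20% to 40% leaves the conclusion unchanged. With only 5 cases the Mann-Whitney threshold rises to 0.77, but the sensitivity interval becomes almost uninformative.

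**What to change.** 1. **Reconcile the OGTT reference categories first.** The plan says "a fasting blood glucose (FBG) below 126 or 2-h blood glucose (2hBG) < 140 mg/dl is considered normal glucose tolerance" but also places "FBG of 100-125 mg/dl or 2-h blood glucose" in the prediabetes range, so a fasting value of 100–125 mg/dl fits both. The reference cannot be assigned until these are reconciled.
2. **Primary analysis.** ROC AUC with 95% CI for one CGM metric, named by the sponsor in advance, against an OGTT-only reference.
3. **Accuracy at a cut-off.** Report sensitivity, specificity and predictive values with exact CIs. State the cut-off beforehand or, if it is chosen in these data, correct for optimism (for example by bootstrap).
4. **Comparisons among CGM, HbA1c and fructosamine.** All are measured in the same women, so use paired methods such as DeLong or exact McNemar, not an unpaired chi-square. Present them as estimates with CIs: with 15 cases, McNemar on sensitivity needs at least 6 discordant pairs all in one direction (2 × 0.5⁶ = 0.031; 5 pairs give 0.0625).
5. **Secondary.** Keep the correlations and group comparisons.
6. **Conclusion.** Word it as concurrent detection of dysglycemia, because participation of up to 10 days cannot show later development of diabetes.

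The cost is SAP wording and a few more analyses of data already being collected, with no extra visits or participants. The downside is that the wide intervals become visible.
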